5.5 Discontinuation of Treatment Criteria

Participants will be discontinued from the treatment if they cannot continue the study safely based on any of the following criteria:

- (1) experience worsening in depression, defined as an increase in HRSD-24 score from baseline of more than 30% on two consecutive assessments;
- (2) experience clinically significant increase in suicidal ideation with imminent intent (based on the SSI) or attempt suicide;
- (3) develop clinically significant hypomanic or manic symptoms
- (4) withdraw consent
- (5) missed seizures (i.e. no induced seizure) on 2 consecutive treatment sessions despite parameter and anaesthesia optimization
- (6) non-compliant with treatment schedule (i.e. miss more than two scheduled treatments)

Participants who are non-compliant with the treatment regimen or who experience two missed seizures on two consecutive occasions despite optimization of anesthesia and treatment parameters will not be discontinued from the trial, but will continue to be followed and will complete assessments to the extent possible contingent upon patient agreement consistent with an intention to treat approach.

Patients who are not able to complete the biomarker testing will be able to complete the clinical portion of the trial and will not be excluded.

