5.7 Data Collection and Statistical Considerations

5.7.1 Power Calculations for primary hypotheses

The primary objective of this trial is to assess the efficacy and cognitive adverse effects of RUL-UB ECT and MST in patients with severe depression in a randomized, multi-centre, non-inferiority clinical trial. We will use a combined primary effectiveness endpoint: (1) MST will result in remission rates on the 24-item Hamilton Rating Scale for Depression (HRSD-24) that is non-inferior to that of RUL-UB ECT; **AND** (2) MST will have a superior cognitive adverse effect and tolerability profile compared to RUL-UB ECT assessed with the AMT. However, our sample size calculation will be based on non-inferiority trial calculations that are sufficiently large enough to minimize Type II error[103] and are consistent with previous large, multi-centre ECT trials[9]. RUL-UB ECT can achieve remission in about 50% of patients with a treatment resistant form of depression[10]. Non-inferiority trials such as this proposed study specify a tolerance threshold, with a tolerance of 15% denoting equivalence between the two treatments when the effectiveness of MST can be concluded to be not less than 35%. The total sample size is derived as a function of tolerance and power with a significance level of 0.05. Using these methods, a total sample size of 260 participants (130 per group) will yield 80% power to confirm a non-inferior difference in HRSD-24 remission rates of 15% between the two study groups. This sample size would also provide >95% power to detect a minimally important difference $\geq 25\%$ (absolute risk difference) change on the AMT total score. The primary analysis will proceed once a minimum of 260 participants achieve a clinically determined adequate trial of treatment. We will define a completer as any participant who has received an adequate trial of RUL-UB-ECT or MST as per the definition used in the literature by Sackeim and colleagues [10] (i.e., 8 treatments or meet remission criteria). The overall rate of dropout in a similar past trial at CAMH was less than 3 percent in those receiving fewer than 8 treatments. As such, the sample size of 260 completers will be attainable. Testing of the cognitive outcome will only proceed if non-inferiority is established on remission. This closed testing procedure will ensure the Type I error probability for these two outcomes does not exceed 0.05.

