The hypothesis to be tested is $H_0: \pi_{ECT} - \pi_{MST} \geq 0.15$ versus $H_1: \pi_{ECT} - \pi_{MST} < 0.15$ where π_{ECT} and π_{MST} are the probabilities of remission in the ECT and MST groups respectively. The primary comparison will be a one-sided Z-test in difference of proportions, compared against the non-inferiority margin of 15%. The 15% non-inferiority margin was chosen as a remission rate of 35% remains clinically meaningful in this difficult to treat sample and still higher than more conventional, less invasive treatments for treatment resistant depression (e.g., rTMS at about 20 percent remission [106] and 14 percent with antidepressants [107]). The absolute risk difference (difference in proportions) will be calculated along with 90% and 95% confidence intervals, using standard normal approximations. Since intention to treat (ITT) analysis introduces a conservatism that is undesirable for non-inferiority trials both ITT (i.e. all randomized participants) and completer analyses (i.e. 8 treatments or met remission criteria) will be performed. The primary analysis for Stage 1 will be a completer analysis and a sensitivity analysis will be done secondarily. Inverse probability weighted methods will be employed in an attempt to attenuate the bias resulting from the improper sub-group that a PP results in. We plan to collect the primary outcome data from all patients regardless of treatment compliance to minimize missing data in the outcomes. If outcomes are missing in more than 5% of the patients in the ITT analysis, inverse probability weighting and multiple imputation approaches will be employed to assess and mitigate the effect of missing data. Multiple Imputation by Chained Equations (MICE) will be used to perform the imputations and the following variables will be used in the missing data model: number of failed antidepressant trials, duration of most recent depressive episode, number of major depressive episodes, benzodiazepine use, age, and presence of the other psychiatric comorbidities, e.g. anxiety, duration of illness, not taking psychiatric medication at baseline, treatment duration, and minority racial status. The number of replications for multiple imputations will be based on the proportion of data that is missing, e.g. 10% missing implies 10 replications. For the inverse probability weighting, weights will be estimated from a logistic regression model (with binary dependent variable: dropout vs not dropout) predicting probability of dropout. In order to have a correctly specified model, most of the baseline variables collected will be included (e.g. demographic and clinical characteristics, HRSD score, SSI score, CGI score, ATHF, BSI score, presence of medical and/or psychiatric comorbidities, etc.). It is only necessary for non-inferiority to be established in the unadjusted analysis described to proceed to the stage 2 analysis although additional secondary analyses of this outcome will be performed.

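### The listed imputation variables for the Stage 1 ITT analysis omit treatment arm and every HRSD-24 rating; imputing remission without arm shrinks the risk difference, which favours non-inferiority

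*Combined protocol and SAP*

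**What the plan says.** Section 5.8.1 (Stage 1) makes the completer analysis primary and adds an ITT analysis of everyone randomised. If more than 5% of ITT outcomes are missing, both multiple imputation by chained equations and inverse probability weighting are to be used.

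- **Imputation.** The inputs are given as a list: "the following variables will be used in the missing data model: number of failed antidepressant trials, duration of most recent depressive episode", then number of episodes, benzodiazepine use, age, psychiatric comorbidity, length of illness, being off psychiatric drugs at baseline, length of treatment and minority status. Arm, site and HRSD-24 at any time point are not named, and imputing within arm is not mentioned. The number of imputations equals the percentage missing.
- **Weighting.** Weights come from a logistic model for dropout: "In order to have a correctly specified model, most of the baseline variables collected will be included". The examples include HRSD score and the list is left open. Arm and on-treatment ratings are not named. The section also calls for weighting to reduce bias in the completer set, without the 5% trigger, and describes no other weight model.
- **Data available.** Section 5.1.5 schedules clinical ratings at baseline, after every three (or four) treatments, and within four days of the last session.
- **Gate.** Stage 2 proceeds if the unadjusted Stage 1 analysis shows non-inferiority.

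**The concern.** An imputation model should contain the comparison that the analysis will make. If arm is left out, a missing participant is given a remission probability pooled over both arms, so the imputed part of the data shows no arm difference by construction. In a superiority test that costs power. In a non-inferiority test it moves the estimate away from the margin and towards the conclusion the trial seeks. The ITT result is the Stage 1 analysis that keeps all randomised participants, so it is the natural check on the completer result and should not lean one way.

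Leaving out HRSD-24 is a different weakness. Interim ratings are likely to be the best predictors of final remission. Without them the missing-at-random assumption is harder to defend and information is lost, but this omission alone sets no direction of bias.

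**Working it through.** **Inputs.** ECT remission of 50%, from section 5.7.1: "RUL-UB ECT can achieve remission in about 50% of patients with a treatment resistant form of depression". A margin of 15 points, so MST is at 35% on the boundary (5.7.1). Alpha of 0.05 (5.7.1), one-sided (5.8.1). 130 per arm: "a total sample size of 260 participants (130 per group) will yield 80% power to confirm a non-inferior difference in HRSD-24 remission rates".

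**The plan's own figure.** The documents give no number for the missing-data method, so the design figure is the one to reproduce.

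- 50% in both arms: power = Φ(0.15/√(0.50/130) − 1.645) = Φ(2.419 − 1.645) = 78.0%.
- Variance taken at 50%/35%: 0.25 + 0.2275 = 0.4775, and power = Φ(0.15/√(0.4775/130) − 1.645) = 79.7%.
- One-sided 0.025 with 50% in both arms gives 67.7%.

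The stated 80% is therefore consistent with a one-sided 0.05 test, which is used below.

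**Expected shrinkage.** Let m be the missing fraction, equal in both arms and completely at random. Without arm, the imputed probability is about (0.50 + 0.35)/2 = 0.425 in each arm.

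- ECT: (1 − m)(0.50) + m(0.425)
- MST: (1 − m)(0.35) + m(0.425)
- Difference: (1 − m)(0.15)

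At m = 0.10 this is 0.4925 − 0.3575 = 0.135.

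**Simulation at the margin.** 50% versus 35%, 130 per arm, imputations equal to the percentage missing, Rubin's rules, 40,000 trials per row. Covariates other than arm are taken as uninformative. The missing fractions are assumptions.

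| Missing | (1 − m) × 15 | Estimate, arm omitted | Type I, arm omitted | Type I, arm included |
|---|---|---|---|---|
| 6% | 14.1 | 14.1 | 5.4% | 5.0% |
| 10% | 13.5 | 13.5 | 5.9% | 4.8% |
| 15% | 12.75 | 12.8 | 6.5% | 4.9% |
| 20% | 12.0 | 12.0 | 7.1% | 4.9% |
| 30% | 10.5 | 10.5 | 8.9% | 4.9% |

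With arm included the mean estimate is 15.0 points throughout. The Monte Carlo standard error of a 5% rate is √(0.05 × 0.95/40,000) = 0.1 point. Type I error rises less than the bias suggests because the standard error is too large when arm is omitted (at 10% missing, mean 0.064 against an actual spread of 0.058). With unequal random loss (MST 20%, ECT 5%) the arm-free estimate is 13.0 points and type I error 6.2%.

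**Weights.** A 4,000-trial simulation per setting used weights from one baseline covariate, without arm:

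- Loss at random or dependent on baseline: 14.9 points against a true 14.9.
- Non-remitters lost more, equally in both arms (25% against 5% of remitters): 15.1 against 14.8.
- Non-remitters lost more on MST (30% against 10% on ECT; remitters 5%): 8.8 against 14.8.

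The direction follows the assumed loss, as the unweighted observed rates show:

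- Loss as in the last setting: 0.475/0.925 − 0.3325/0.7875 = 0.514 − 0.422 = 9.1 points.
- Same rates with the arms exchanged: 0.475/0.825 − 0.3325/0.9175 = 0.576 − 0.362 = 21.3 points, which counts against MST.

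**The case against.** **Arm may be understood.** The covariate list for the adjusted analysis, also in 5.8.1, does not name arm either, yet that model must contain it to give an arm odds ratio. The imputation list repeats its four clinical covariates and does not name remission, the variable being imputed. So arm may be taken for granted. This reading is possible, and the omission of arm is certain only if the list is followed literally. It does not explain the absence of HRSD-24, which the weighting passage names where it is wanted.

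**Reach and size.** The imputation is conditional, secondary and outside the gate. Section 5.7.1 cites dropout below 3% in a similar past trial, which would not trigger it. That stands as to reach, although the figure concerns participants with fewer than 8 treatments at one site and is not a missing-outcome rate for this trial. Inflation at 6% to 10% missing is below one percentage point.

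**Treatment duration is listed** and may carry some information on clinical course. It does not replace arm.

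**Stronger readings that the documents do not support:**

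- *That someone stopped for worsening is imputed an average chance of remission.* The stopping rule in 5.5 is "experience worsening in depression, defined as an increase in HRSD-24 score from baseline of more than 30% on two consecutive assessments". Such a participant already has ratings, is due another within four days of the last session, and falls under the 5.8.1 plan to collect the primary outcome whatever the compliance. The outcome would usually be an observed non-remission.
- *That failures lost mainly from MST make the bias much larger.* With 3% of ECT and 10% of MST participants lost, all failures, the arm-free model gives (0.50 + 0.03 × 0.4545) − (0.35 + 0.10 × 0.4545) = 11.8 points. With arm included it is still 0.50/0.97 − 0.35/0.90 = 12.7, so about 2.3 of the 3.2 points of bias come from the assumed loss. Exchanging the loss rates gives 18.2 points. Nothing in the documents supports either pattern.
- *That the weights also pull towards no difference.* Weighting imputes nothing, and the check above shows no fixed direction.

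**Conclusion.** The point holds, with limited reach. As written, the imputation list leaves out arm, site and all HRSD-24 ratings. Applied literally, it reduces a true 15-point deficit to about 14.1, 13.5 and 12.0 points at 6%, 10% and 20% missing, with one-sided type I error of about 5.4%, 5.9% and 7.1% against a nominal 5%. These figures rest on outcomes missing completely at random, uninformative covariates and assumed missing fractions. Informative baseline covariates would not remove the shrinkage.

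The error favours non-inferiority in the ITT sensitivity analysis. A reader might infer that it could produce the primary conclusion. It cannot, because the unadjusted completer test and the Stage 2 gate do not use the imputed data. The weight model's silence on arm and on-treatment course is a separate gap, of unknown direction, and it carries over to the weighted completer analysis. Overall the point is below must-fix, but it is a concrete error of specification and should be corrected before unblinding.

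**What to change.** In 5.8.1:

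1. Run the imputation separately by arm, or state that arm is in the model. Add site, baseline HRSD-24 and all observed on-treatment HRSD-24 ratings to the listed variables.
2. Add arm and on-treatment HRSD-24 up to dropout to the weight model, and say whether the same model serves the completer set.
3. Where Stage 2 secondary analyses follow the Stage 1 approach, use the same structure with baseline AMT. In that superiority test, shrinkage would work against MST.

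How participants who stop treatment are classified, and whether remission is imputed directly or derived from imputed scores, are estimand and method choices for the sponsor. This correction does not depend on them.

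The cost is a few lines of SAP text and slightly more analysis work. No new data are needed.

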1.1.3. Magnetic Seizure Therapy (MST) is a New Convulsive Neuromodulation Therapy

MST is an alternative form of convulsive therapy, that like ECT, involves the induction of a seizure to achieve a therapeutic response[22]. However, the induction of a seizure occurs through the use of high frequency, rTMS rather than high frequency, repetitive transcranial electrical stimulation. With magnetic stimulation, a rapid, high intensity, time varying magnetic field is able to pass into the brain without resistance and stimulate neurons thereby limiting seizure spread as the induced magnetic field can be focally targeted based on geometry of the stimulating magnetic coil[32, 33]. Additionally, the magnetic field is not impeded nor shunted by non-conducting material (i.e., skull) and, therefore, the field results in focal brain activation[34, 35]. Specifically, compared to right unilateral ultrabrief pulse ECT (RUL-UB-ECT), the electric field induced by MST is 5–10 times more focal[35, 36].

In an early study, White et al. compared 20 patients with severe depression openly allocated to receive ECT or MST. In the MST relative to the ECT group, time to orientation was much shorter (4 vs. 18 minutes, $p < 0.01$). The Hamilton Rating Scale for Depression-24 item (HRSD-24) score improved from 32 to 14 in the MST group, while in the ECT group the score improved from 30 to 6[37]. In another study, 20 TRD patients were allocated to receive either right unilateral (RUL) ECT or MST. Comparable antidepressant response and no cognitive side effects were observed in both groups[8]. Note that in the latter study, RUL ECT was administered at 3 times the seizure threshold, which reduced the cognitive side effects, but might hinder the response to ECT. A subsequent MST study done by the same group collated the data from the former study with 16

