5.0 APPROACH

5.1.1 Research Design and Methods

The trial will be registered in an international clinical trial registry (clinicaltrials.gov) and results will be reported in a manner consistent with the international CONSORT guidelines. The study will involve a randomized, double blind, parallel-group clinical trial with two treatment arms conducted at three leading academic institutions in North America: CAMH, University of Texas Southwestern in Dallas, and University of California, San Diego (UCSD). Based on our power analysis (Section 5.7.1), a total of 260 participants with depression will be randomized to receive MST or RUL-UB-ECT. We plan to enroll four to five participants per month across the three study sites over 54 months.

Treatment will be administered two to three days per week. Depression symptoms will be assessed with the 24-item Hamilton Depression Rating Scale (HRSD-24) [74] and suicidality will be assessed with the Scale for Suicidal Ideation (SSI) [69]. Remission will be defined as HRSD-24 ≤ 10 and a $> 60\%$ decrease in scores from baseline on two consecutive ratings. Once a participant reaches remission, a second rating to confirm remission will be conducted immediately before their next scheduled treatment. If remission is confirmed, they will then be considered a completer of the acute treatment course. Remission of suicidal ideation is defined as a score of 0 on the SSI. Therefore, there will be no specific minimum number of treatments that patients must receive to be classified as remitters. However, patients who do not meet remission criteria after 21 treatment sessions will be considered non-remitters and will cease treatment sessions. This maximum treatment number was chosen allowing for the possibility that MST may require more treatment sessions to achieve remission, similar to RUL-UB ECT [29-31]. The blind will not be broken to participants until the completion of the entire study. Following completion of the acute treatment course, participants who achieve response (defined as a 50% reduction in symptoms on the HRSD-24 from baseline) or remission will be referred to a maintenance treatment trial.

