5.1.5 Clinical and Cognitive Measures

Screening and Baseline evaluation:

Prior to screening, potential participants will be seen for a consultation by an ECT/MST attending psychiatrist. Capacity to consent to treatment and research procedures will be assessed and documented. Participants will be screened with the MINI V 6.0 and HRSD-24 to determine eligibility. The MINI V 6.0 assesses current and lifetime depression and other psychiatric disorders. It will be used to clarify psychiatric inclusion and exclusion criteria. Furthermore, a score of greater than or equal to 21 on the HRSD-24 will be used to establish eligibility. The Transcranial Magnetic Stimulation Adult Safety Screen will be used to assess for potential MST risk factors[75]. The Antidepressant Treatment History Form (ATHF) will be used to quantify level of treatment resistance[77, 78]. Demographic information, medical history and concomitant medications information will also be collected at the screening visit. The Clinical Global Impression Scale-Severity (CGI-S)[46] and Young Mania Rating scale (YMRS) will also be completed at baseline. The schedule of assessments is depicted in Table 1 (Appendix A).

Clinical Assessments During and After Treatment:

Clinical outcome measures will be completed at baseline, after every three treatments (or every four treatments to facilitate treatment scheduling) immediately prior to the next treatment session, within four days of the last treatment session, and then six months post-treatment. This latter time point will be part of an exploratory analysis to study the long-term clinical and cognitive outcomes post- ECT or post-MST treatment. The HRSD-24 [74] will be the primary outcome measure. Secondary outcome measures will include the Scale for Suicidal Ideation (SSI)[69], Brief Symptom Inventory (BSI)[79], Clinical Global Impression Severity/Improvement Scale (CGI-S, CGI-I)[80], Quality of Life Enjoyment and Satisfaction Questionnaire (Q-LES-Q)[81], and the Columbia ECT Subjective Side Effects Schedule[82].

Cognitive Assessments

The cognitive battery was designed to comprehensively examine cognitive dimensions that are affected by seizure therapies while minimizing burden on participants[23]. Assessments included in the cognitive battery measure global cognitive function, intellectual abilities, attention, processing speed, verbal fluency, anterograde and retrograde memory, and executive functions. Specific cognitive measures include:

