
An adjusted analysis will be performed using generalized linear models for binary data. Study site will be included as well as clinical variables known to be associated with remission (see again Senn et al.[105] and Pocock et. al.[104]). The following variables will be included in the analysis, which have been shown to be related to response/remission in this population: number of failed antidepressant trials, duration of most recent depressive episode, number of major depressive episodes, and benzodiazepine use (in lorazepam equivalents). The purpose of the adjusted analysis is to ensure the non-inferiority finding is consistent between an unadjusted analysis and one in which predictors of outcome are controlled for. This consistency will be examined in two ways. First, the unadjusted odds ratio and 95% confidence interval will be compared with the adjusted for consistency. Second, the fitted logistic regression model will be used to estimate the probability of response for each subject. An adjusted difference in proportions will be estimated by averaging the predicted probabilities within group and taking the difference. A bootstrap will then be used to generate a distribution of this measurement from which the bias corrected percentiles can be obtained to compare with the 15% non-inferiority margin.

Stage 2 Analysis

In terms of cognitive superiority, we will use the autobiographical memory test (AMT). The binary outcome is defined as a worsening of $\geq 25\%$ on the AMT total score. The hypothesis to be tested is $H_0: \pi_{ECT} - \pi_{MST} = 0$ versus $H_1: \pi_{ECT} - \pi_{MST} \neq 0$ where π_{ECT} and π_{MST} are the probabilities of deterioration in the ECT and MST groups respectively. This primary analysis will be ITT. The hypothesis will be tested with a chi-square test. The absolute risk difference and 95% confidence interval will be computed using standard methods. Secondary analyses will follow a similar approach as in stage 1.

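### Every specified between-arm HRSD-24 comparison uses remission yes/no, and the adjusted remission model leaves out baseline HRSD-24

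*Combined protocol and SAP*

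**What the plan says.** Section 5.1.5 states: "The HRSD-24 [74] will be the primary outcome measure". Ratings are scheduled at baseline, after every three or four treatments, within four days of the last treatment, and at six months. Section 5.1.1 turns the scale into remission: a score of 10 or less together with a more than 60% "decrease in scores from baseline on two consecutive ratings".

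Section 5.8.1 then sets the Stage 1 test: "The primary comparison will be a one-sided Z-test in difference of proportions, compared against the non-inferiority margin of 15" per cent. The completer, ITT, weighted and imputed versions all concern the same binary outcome. The adjusted analysis is a generalized linear model for binary data with site plus "number of failed antidepressant trials, duration of most recent depressive episode, number of major depressive episodes, and benzodiazepine use (in lorazepam equivalents". Its stated purpose is to see whether the non-inferiority finding holds once predictors of outcome are controlled. The HRSD score is named in one model only, the dropout model that supplies the inverse probability weights.

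Section 5.8.2 covers remission on the SSI, and sections 5.8.3 to 5.8.5 contain no HRSD-24 comparison between arms. Response (a 50% reduction) is defined in section 5.1.1 for referral to a maintenance trial, not for analysis.

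**The concern.** There are two separate gaps.

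First, a binary endpoint treats a final score of 11 and a final score of 35 alike. With remission expected in about 50% (section 5.7.1), or about 60% on the figure in section 5.8.2, some 40-50% of patients fall into one undifferentiated category. A finding of non-inferior efficacy would then carry no specified information on how those patients fared on the trial's own primary scale, even though the scores are collected.

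Second, the adjusted model is meant as a robustness check with outcome predictors controlled, but it omits the one baseline variable that is built into the definition of the outcome.

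The two gaps need different remedies. A baseline covariate in a remission model says nothing about non-remitters' scores; only an analysis of the score does.

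**Working it through.** **1. The plan's own figure.** Inputs from sections 5.7.1 and 5.8.1: 130 per arm, 50% remission in both arms, margin 0.15, one-sided test "with a significance level of 0.05".

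- SE = sqrt(2 × 0.5 × 0.5 / 130) = 0.0620.
- Power = Φ(0.15/0.0620 − 1.645) = Φ(0.774) = 78.0%.
- Exact binomial enumeration of the same test: 79.0%. At 60% remission in both arms: 79.5%.
- Variance taken at the margin (50% against 35%): 79.7%.

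The stated 80% is reproduced closely enough. It rests on one-sided 0.05; one-sided 0.025 would give 67.7%.

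**2. What the test can see.** The statistic is a function of the two remission counts only. The 79% is therefore the same whatever the non-remitters' scores are.

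**3. Illustrative size.** The documents give no HRSD-24 SDs or end-of-course means, so all of these are assumptions: 50% remission in both arms; remitters mean 6, SD 3; ECT non-remitters mean 20, SD 8; MST non-remitters mean 28, SD 8.

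- Mean difference over all patients = 0.5 × 8 = 4 points.
- Variance in an arm = 0.5 × 3² + 0.5 × 8² + 0.25 × (non-remitter mean − 6)². ECT: 36.5 + 49 = 85.5. MST: 36.5 + 121 = 157.5.
- SE = sqrt((85.5 + 157.5)/130) = 1.367.
- Power, two-sided 0.05 = Φ(4/1.367 − 1.96) = Φ(0.966) = 83%.

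A simulation of 4,000 trials per row used other assumptions (baseline mean 29, SD 5; remitters about 6; ECT non-remitters about 21, SD 7) and adjusted the score for baseline:

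| MST non-remitter deficit (points) | Stage 1 passes | Score analysis shows MST worse | Both |
|---|---|---|---|
| 0 | 78.3% | 2.8% | 0.1% |
| 4 | 78.8% | 33.5% | 14.3% |
| 6 | 77.9% | 61.5% | 39.6% |
| 8 | 78.4% | 81.2% | 59.6% |
| 10 | 78.8% | 92.7% | 71.4% |

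**4. Baseline in the remission rule.** A fall of more than 60% means a final score below 0.4 × baseline, and the score must also be 10 or less. In whole points the highest remitting score is:

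- baseline 21-22: 8
- baseline 23-25: 9
- baseline 26 or more: 10

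The fall needed is 13 points from 21 (62%), 20 from 30 (67%) and 30 from 40 (75%).

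**5. What each remedy yields.** Adding baseline HRSD-24 to the remission model gains about 0-3 points of power under assumed baseline-to-end correlations of 0.2-0.4. For the score ANCOVA, the 95% half-width is 1.96 × SD × sqrt(1 − r²) × sqrt(2/130). That is 1.7 points at SD 8, r 0.5, and 2.9 points at SD 12, r 0.

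**The case against.** Remission is a legitimate primary endpoint, and the 15% margin is argued on the remission scale. The step to Stage 2 depends only on the unadjusted test, so nothing here alters the trial's decision. The covariate list follows a stated rule, namely variables shown to relate to response or remission in this population. The 8-point scenario, with remission exactly equal, is constructed to be invisible to a binary test. If the arms instead differ by a shift of the whole score distribution, the supportive analysis seldom adds anything. Given a Stage 1 pass with ECT at 50%, its interval excludes zero against MST in about 1% of trials at a true MST remission of 45%, 3% at 42.5% and 7% at 40%. All of this stands, and it limits the point to a supporting analysis.

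A reader might also infer stronger things that the documents do not support:

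- *That omitting the baseline covariate is what hides a non-remitter deficit.* It is not; a remission model cannot show non-remitters' scores with or without it.
- *That nothing in the plan could show such a deficit.* BSI, CGI and Q-LES-Q are collected after the acute course, and an exploratory six-month analysis is planned. Their between-arm models are simply not specified.
- *That the early comparison cited in section 1.1.3 shows the deficit:* "score improved from 32 to 14 in the MST group, while in the ECT group the score improved from 30 to 6". It had 20 openly allocated patients, reports whole-group means, and starts from different baselines, so the changes are 18 and 24 points. The same section cites a second comparison with similar response.
- *That the score should replace remission because it is more powerful.* That depends on how the arms differ, and the margin has been justified only for remission.

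**Conclusion.** The point holds as a gap in the supporting analyses and does not invalidate Stage 1. No between-arm analysis of the HRSD-24 score is specified, and the adjusted remission model omits a baseline value on which the endpoint depends. Stage 1 passes about 79% of the time at 50% remission in both arms, regardless of non-remitters' scores. If MST non-remitters ended 8 points worse, a score comparison would detect it in about 81-84% of trials, and a Stage 1 pass together with a detected deficit would occur in about 60-63%.

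The 79% rests on the plan's own inputs. The detection figures rest on assumed means, SDs and baseline correlation; they illustrate what the analysis could show and do not forecast that such a deficit exists. The share of non-remitters is about 50% from section 5.7.1. The 40% comes from section 5.8.2, which discusses the SSI endpoint and does not name the scale for its 60%. The change is worth making because it is cheap and because a score analysis added after the results are known would carry less weight.

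**What to change.** Keep remission and the 15% margin as the Stage 1 decision.

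1. In the adjusted analysis of section 5.8.1, add baseline HRSD-24 as a continuous covariate, using the same pre-treatment rating that the remission rule uses. This aligns the check with the endpoint.
2. Pre-specify one supportive analysis: end-of-acute-course HRSD-24 total by ANCOVA on arm, baseline HRSD-24 and site, in both the ITT and completer sets. Report the mean difference with its 95% confidence interval beside the remission difference. The comparison should be between whole arms, because non-remitters are a subgroup formed after randomisation. State that the final rating falls at outcome-dependent times, since treatment ends at confirmed remission or after 21 sessions.

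No automatic rule should tie the wording of the conclusion to whether this interval excludes zero, because the plan has no clinical margin for the score.

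Cost: SAP wording and one extra model on data already collected, with no change to sample size or alpha. The downside is a second efficacy estimate that may temper a positive result.
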